#### 9.4.3 REPORTING UNANTICIPATED PROBLEMS TO PARTICIPANTS

N/A

---

## 10 STATISTICAL CONSIDERATIONS

We will publicly register this protocol with ClinicalTrials.gov prior to study recruitment; it contains all details regarding statistical analysis and so there will be no separate statistical analysis plan.

---

### 10.1 STATISTICAL HYPOTHESES

---

#### 10.1.1 PRIMARY ENDPOINT:

We hypothesize that GogyUp Reader app use with written patient education materials or self-care instructions will result in better health literacy compared with print patient

education or care plan materials alone. Alternatively, our null hypothesis is that there will be no difference in health literacy.

#### 10.1.2 SECONDARY ENDPOINTS:

We hypothesize that GogyUp Reader app use with written patient education materials or self-care instructions will result in better patient self-management of diabetes compared with print patient education or care plan materials alone. Alternatively, our null hypothesis is that there will be no differences in secondary endpoints.

### 10.2 SAMPLE SIZE DETERMINATION

Due to lack of literature on meaningful effect size for our primary effectiveness outcome, our power calculation is based on a general effect size, the standardized mean difference (SMD). SMD consists of the mean difference in the outcome between arms, divided by the standard deviation of the outcome in the control arm, with moderate effect size being SMD=0.5 and large effect size being SMD=0.7. Based on information in the original validation paper, mean Understanding subscale summary score was 3.85, standard deviation 0.74. With 60 subjects per arm (a low estimate), we will have 78% power to detect a moderate effect size (a between-group difference of .37 on the scale, SMD=0.5) and 97% power to detect a large effect size (SMD=0.7, difference of .52) based on performing a two-sample t-test comparing the treatment arms. With differences in post means of 0.3 and 0.5, power will be 60% and 96%, respectively. However, we want to help insure against difficult recruitment as well as, in particular, a potentially smaller effect size, which can have a large impact on sufficient power. Therefore, our targeted enrollment is 80 per arm (n=160), which would support 73% power for a .3 difference in post means (modest of SMD of .405), with attempted recruitment of up to 200 (given a possible 20 percent recruitment/screening failure rate). Individuals who withdraw or otherwise lost to follow-up will be included in the analysis (see below re: attrition). Regarding our other primary endpoint, for the having sufficient information subscale, (mean 2.98, standard deviation .54), 80 participants per arm would provide 72% power to detect a modest SMD of .40 and 60 participants would provide 78% power to detect a SMD of .5. For our secondary outcome, the perceived diabetes self-management scale (mean 2.585, standard deviation .455), 80 participants per arm would provide 72% power to detect SMD=.4, and 60 participants would likewise provide .78 power to detect SMD=.5.

### 10.3 POPULATIONS FOR ANALYSES

Study population will include only intention-to-treat (as randomized).

### 10.4 STATISTICAL ANALYSES

#### 10.4.1 GENERAL APPROACH

For descriptive statistics, we will present percentages for binary variables, and medians and means (with standard deviations and overall ranges) for continuous variables. For

inferential tests, marginal p-value and confidence intervals for statistical significance (using two-tailed tests) will be  $p < .05$  and 95% confidence, respectively. We will specify covariate and other design information below.

---

#### 10.4.2 ANALYSIS OF THE PRIMARY ENDPOINT(S)

We will specify the primary outcome as three-month follow-up level of the Health Literacy Questionnaire subscales 9 and 2 (understanding written information and having enough in enough information) as single endpoints (not repeated measures)..

We will compare the mean outcomes at follow-up between the treatment arms using analysis of covariance (ANCOVA), which compares follow-up outcome values between study arms while controlling for the baseline levels to gain power to detect an effect. The primary analysis will be an intent-to-treat (ITT); for non-monotonic missing (e.g., missing a baseline value), we will use multiple imputation with pattern mixture model adjustments in sensitivity analyses allowing for plausible differences among the missing—the justification for this is that pattern mixture models allow for a Missing Not At Random assumption, which is plausible in this case because we will not have measures for all likely variables associated with missingness. Pattern mixture models allow for us to set plausible values for missingness at both high or low levels to obtain a range of outcome estimates allowing for plausible missing data scenarios. For any monotonic missing—i.e., attrition (withdrawal or other lost to follow-up), we will use last observation carried forward but will also conduct sensitivity analyses using pattern mixture models under plausible assumptions of missing data patterns. We will present results using adjusted (least-squares) means with standard errors, p-values, and 95% confidence intervals. Baseline levels of endpoint outcomes will be included as a covariate to gain power to detect an effect, a standard use of ANCOVA.

---

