**Grant**

**Number:**

1R43NR020340

**Study Description:** This protocol describes a pilot randomized controlled trial to test the primary hypothesis that a mobile application, GogyUp Reader, will result in higher health literacy in understanding print diabetes patient education materials than print patient education and care plan materials alone.

**Objectives\*:** The **primary objective** of this study is to conduct a pilot trial of the effect of the GogyUp Reader app on health literacy.

The **secondary objectives** are to assess the effect of GogyUp Reader on perceived diabetes self-management.

**Endpoints\*:** **Primary Endpoint:** three-month (follow-up) scores on two subscales of the Health Literacy Questionnaire: Subscale 9: Understanding health information well enough to know what to do (“Understanding health information”); Subscale 2: Having sufficient information to manage my health (“Having sufficient information”).

**Secondary Endpoints:** three-month (follow-up) score on the Perceived Diabetes Self-Management Scale (PDSMS)

**Study Population:** The maximum sample size is up to 200 individuals, with expectation of potential non-contact by patients after a recruitment mailing, screening failures and refusal bringing likely sample size down to approximately 120-160. The target population are individuals aged 18-85 diagnosed with type 2 diabetes mellitus seen at clinics serving large proportions of low-income patients (e.g., safety net clinics). We will attempt to sample up to 200 individuals from the MHealth Fairview health system in the seven-county Twin Cities Metropolitan area.

**Phase\* or Stage:** Although the proposed trial is not of a pharmaceutical or other therapeutic treatment, it most resembles a phase 2 trial in that we have early preliminary data of use and feasibility and are testing initial efficacy.

**Facilities Enrolling Participants:** Study activities will not take place in any clinical sites; participants will be identified based on having been seen for a clinic visit to a primary care clinic within the partnering health system and will receive a mailing from the health system providing contact

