## 5 STUDY DESIGN

### 5.1 OVERALL DESIGN

#### Hypotheses:

H1: GogyUp Reader app use with written patient education materials or self-care instructions will result in better health literacy in understanding health information compared with print patient education or care plan materials alone.

H2: GogyUp Reader app use with written patient education materials or self-care instructions will result in better health literacy in reporting having enough information compared with print patient education or care plan materials alone.

H3: GogyUp Reader app use with written patient education materials or self-care instructions will result in better diabetes self-management compared with print patient education or care plan materials alone.

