#### 10.4.6 PLANNED INTERIM ANALYSES

We will conduct an interim analysis of the primary endpoints to provide data for a SBIR Phase II application, likely six months into the study period. The analysis, while lower-powered, will be the same analysis as described in 2.4.2 above. The interim analysis will not prompt study discontinuation or participant withdrawal by the investigators. Type I error will be addressed in the final analysis as described in 2.4.2.

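### Two HLQ subscales are both primary and each is tested at a marginal two-sided .05 against a single health-literacy null, with no rule on whether one or both must succeed

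*Combined protocol and SAP*

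**What the plan says.** - **Two primary endpoints.** Section 10.4.2: "We will specify the primary outcome as three-month follow-up level of the Health Literacy Questionnaire subscales 9 and 2". It analyses them "as single endpoints (not repeated measures"), each by ANCOVA on the follow-up score adjusted for baseline.
- **Test level.** Section 10.4.1: "marginal p-value and confidence intervals for statistical significance (using two-tailed tests) will be" p < .05 and 95% confidence.
- **One null.** Section 10.1.1 does not split the hypothesis by subscale: "our null hypothesis is that there will be no difference in health literacy".
- **Two hypotheses.** Section 5.1 gives one per subscale. H1 says that use of the app "will result in better health literacy in understanding health information compared with print patient education"; H2 says that it "will result in better health literacy in reporting having enough information compared with print patient education".
- **Synopsis.** Section 2.1 refers to "the primary hypothesis that a mobile application, GogyUp Reader, will result in higher health literacy in understanding print diabetes patient education materials", which is close to H1.
- **Power.** Section 10.2 powers each subscale on its own.
- **Type I error.** Section 10.4.6, on the interim analysis: "Type I error will be addressed in the final analysis as described in 2.4.2". There is no section 2.4.2. The same paragraph uses that number for the primary analysis, so 10.4.2 is evidently meant. Section 10.4.2 covers ANCOVA, missing data and presentation, and has nothing on Type I error.
- **No other source.** Section 10 says that the protocol holds all analysis details and that no separate SAP will exist.

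**The concern.** With two primary endpoints, a plan has to say what counts as success. Here three readings are possible: either subscale is enough, both are required, or each supports only its own claim. They have different error rates and different power, and the text does not choose among them.

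The single null in 10.1.1 is what makes this more than a missing detail. Two tests at .05 each, either of which could be taken to reject that null, do not hold its error rate at .05. The trial is described as a superiority trial of initial efficacy, and its results feed a later, fully powered trial. A significant result on one subscale alone would leave a reader unable to tell whether the pre-specified criterion had been met.

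Timing adds to this. Under 7.3 the investigators are told which arm is which after the interim analysis, and under 10.4.6 that analysis covers the primary endpoints. A rule written after that point could be chosen with interim results on both subscales in view.

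**Working it through.** **Inputs.** From 10.4.1: two-sided alpha .05, so .025 in the favourable direction and a critical value of 1.96. From 10.2: SD 0.74 for subscale 9, SMD .40 for subscale 2, and 80 or 60 per arm. The correlation between the two test statistics is not in the documents; 0 to 0.9 is assumed.

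**Step 1: reproduce 10.2.** Power ≈ Φ(SMD × √(n/2) − 1.96), with an exact noncentral-t check.
- Subscale 9, 80 per arm, difference 0.3: SMD = 0.3/0.74 = 0.405; 0.405 × √40 = 2.56; Φ(0.60) = 72.7% (t: 72.2%). The plan gives 73%.
- Subscale 2, 80 per arm, SMD .40: 0.40 × √40 = 2.53; Φ(0.57) = 71.6% (t: 71.0%). The plan gives 72%.
- Either subscale, 60 per arm, SMD .5: 0.5 × √30 = 2.74; Φ(0.78) = 78.2% (t: 77.5%). The plan gives 78%.

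The figures reproduce, so each subscale was powered alone at the full .05.

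**Step 2: error rate if either subscale is enough.** Both nulls are true and (Z1, Z2) is bivariate normal with correlation ρ. False favourable: 1 − P(Z1 < 1.96, Z2 < 1.96). Either direction: 1 − P(|Z1| < 1.96, |Z2| < 1.96). At ρ = 0 these are 1 − 0.975² = 4.94% and 1 − 0.95² = 9.75%.

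| ρ (assumed) | False favourable (one test: 2.5%) | Either direction (one test: 5%) |
|---|---|---|
| 0 | 4.94% | 9.75% |
| 0.3 | 4.76% | 9.51% |
| 0.5 | 4.54% | 9.07% |
| 0.7 | 4.17% | 8.35% |
| 0.9 | 3.52% | 7.04% |

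In either direction this is 9.75/5 = 1.95 times nominal at ρ = 0 and 7.04/5 = 1.41 times at ρ = 0.9.

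**Step 3: power if both must succeed.** For 80 per arm with SMDs 0.405 and 0.40, the t-test powers multiply at ρ = 0 to 0.721 × 0.710 = 51.2%; at ρ = 0.9 the joint power is 65.5%. The normal approximation gives 52.0% and 66.0%. About 51 to 66% covers both bases.

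**Step 4: the remedies.** In a fixed sequence, a false significant result on either subscale requires subscale 9 to be significant first. With both nulls true, the chance of any false result is therefore 5%. Subscale 9 keeps its 72%, and a claim on subscale 2 has the joint power of step 3. Under Holm, the first step is at .025, where t-test power at 80 per arm is 61.8% for subscale 9 and 60.6% for subscale 2.

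**The case against.** The strongest case on the other side is that the plan intends separate claims. Section 5.1 states H1 and H2 one per subscale, 10.2 powers each alone, and marginal p-values can be read as a deliberate choice of per-test error. The single null in 10.1.1 might only summarise H1 and H2. On that reading each claim stays at 5% and one clarifying sentence would do. The reading is fair, which is why the error figures above are conditional. It does not settle the matter, because 10.1.1 still states one null and no passage says which statement governs. The phrase about single endpoints in 10.4.2 describes a single time point and is not a success rule.

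Three stronger inferences are tempting, and the documents do not support them:
- A reader might take the Type I sentence in 10.4.6 as a promised correction for two subscales. It sits in the interim section and most naturally concerns the repeated look. What stands is that it points to a section with no error control of any kind.
- A reader might cite the synopsis as backing a claim that either subscale could satisfy. Its wording is about understanding, so it fits H1 and suggests that subscale 9 leads.
- A reader might think that the interim look raises these error rates. It cannot stop the trial, and it adds nothing to the figures here.

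The timing concern is also limited. Section 7.3 uses separate interim identifiers to protect the final blinding, and registration before recruitment together with IRB approval of amendments would make a later change traceable. Both subscales will be reported with confidence intervals, so neither result is hidden.

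**Conclusion.** The point holds in conditional form. Two primary subscales, two marginal .05 tests, one null and no success rule leave the criterion undefined, and the text to which 10.4.6 refers does not supply one. If either subscale is allowed to reject the single null, a false favourable result has a 3.5 to 4.9% chance against 2.5%, or 7.0 to 9.75% in either direction against 5%, for correlations assumed from 0.9 down to 0. If both must succeed, there is no inflation, but the per-subscale power in 10.2 overstates the chance of success.

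It would go too far to say that the plan as a whole runs at nearly 10% Type I error. That needs the either-is-enough reading, zero correlation and counting results that favour print. Since this is a pilot informing a fully powered trial, the consequence is a disputable efficacy signal, not a wrong confirmatory claim. The change is worth making but is not critical.

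**What to change.** Before any unblinded interim result is seen:
- **10.4.2:** specify a fixed sequence at two-sided .05. Test subscale 9 first, and test subscale 2 only if subscale 9 succeeds. Subscale 9 is the natural lead: it is H1, it matches the synopsis wording, and it sets the target of 80 per arm.
- **10.1.1:** replace the single null with one per subscale, aligned with H1 and H2.
- **10.4.6:** correct both references from 2.4.2 to 10.4.2.
- **10.2:** state that subscale 9 keeps about 72% power and that a claim on subscale 2 has about 51 to 66%, for a correlation assumed from 0.9 down to 0 (lowest at 0).
- **Reporting:** still give both estimates with 95% confidence intervals, whatever the outcome of the sequence.

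This takes a few sentences and no extra participants or data. The downside is that a claim on subscale 2 depends on subscale 9. If the sponsor does not want that ordering, Holm is an alternative, at a cost of about 10 points of first-step power at 80 per arm on the t-test basis (72% to 62% for subscale 9, 71% to 61% for subscale 2).

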### 5.3 JUSTIFICATION FOR INTERVENTION

Intervention delivery via mobile software app is precisely central to the potential benefit of the intervention: in-the-moment support for patients' capacity to interact with complex written patient materials. We will only have two actual study contacts beyond recruitment and pre-screen/consenting: baseline and follow-up at three months, which will only include obtaining outcome measurement administration necessary to analyze data to meet our study objectives. We will have app usage data (internal to GogyUp) that can provide any indication as to whether lack of differences between arms in an intent-to-treat analysis is simply due to low app usage (this would provide a finding, and inform future study design, rather than being a failure).

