### 5.4 END-OF-STUDY DEFINITION

Participants will be considered to have completed the study if they have completed the baseline and three-month follow-up assessments.

The end of the study is defined as completion of the 3-month follow-up assessment shown in the Schedule of Activities (SoA), **Section 2.3.**]

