Candidates who enroll and are placed in the intervention group will be asked to use their personal devices. If a participant placed in the intervention group does not have regular, consistent access to an Internet-connected device will be provided a cellular-enabled tablet with an active SIM card for the duration of their participation. Participants who use their own intent-connected devices will be sent a \$25 gift card at baseline to offset network expenses.

All participants, whether they are in the control group or are in the intervention group, will receive a \$25 gift card in compensation at the end of the study period. These measures will assist both with ensuring that the intervention is not hindered by technological or network access barriers and also provide both an incentive to stay enrolled, helping to ensure retention. We will also obtain multiple forms of contact information from consented participants to ensure we can contact them at follow-up. We believe our proximal outcome and short follow-up will further ensure retention and completion.

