#### 10.4.3 ANALYSIS OF THE SECONDARY ENDPOINT(S)

The secondary endpoint will be analyzed and presented in the same manner as the primary endpoint, with the same model assumptions and the same approach to missing data. The analysis will not depend on findings or analysis of the primary endpoint.

The secondary endpoint, like the primary endpoints, is a continuous score.

---

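### The primary analysis fills every drop-out's three-month score with the pre-treatment score (LOCF): an unjustified zero-change assumption that can bias the effect and understates its uncertainty

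*Combined protocol and SAP*

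**What the plan says.** Section 10.4.2 compares three-month scores on HLQ subscales 9 and 2 by ANCOVA, adjusted for baseline, by intention to treat. It names multiple imputation for non-monotonic gaps such as an absent baseline score. For attrition the rule differs: "we will use last observation carried forward but will also conduct sensitivity analyses using pattern mixture models under plausible assumptions of missing data patterns". The section explains that pattern-mixture models let missing values be set high or low to give a range of results, but it does not state the values.

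Section 5.3 limits study contacts after consent to "baseline and follow-up at three months, which will only include obtaining outcome measurement" administration. Section 5.4 defines completion as having "completed the baseline and three-month follow-up assessments". The schedule in section 2.3 agrees.

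Section 10.2 adds: "Individuals who withdraw or otherwise lost to follow-up will be included in the analysis". Section 10.4.3 handles the secondary endpoint "with the same model assumptions and the same approach to missing data".

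The only reasoning about missingness is that a not-at-random mechanism is plausible "because we will not have measures for all likely variables associated with missingness". It is offered in support of the pattern-mixture models. Section 10 says there will be no separate SAP, so this text is where the rule is fixed.

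**The concern.** LOCF is usually debated for trials with several visits, where some post-treatment information is carried forward. Here there is none. Each drop-out with a baseline is entered as having changed by exactly zero, in both arms, with no allowance for the fact that the value is a guess.

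The estimate, p-value and interval for both primary endpoints rest on that assumption, and the plan does not defend it. Saying that missingness may depend on unmeasured factors does not support it either, because zero change is only one of many not-at-random possibilities. Section 5.1.3 gives efficacy estimates as the overall goal, so the size of the estimate and the honesty of its interval matter as much as the test.

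**Working it through.** **Inputs from the documents.** SD 0.74 for subscale 9 and 0.54 for subscale 2; target 80 per arm; difference of interest 0.30 on subscale 9 (all section 10.2); two-sided 5% (10.4.1).

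**Assumed, because the documents give no value.** Drop-out by arm, mean change over three months, and baseline to follow-up correlation r (0.5 unless stated). The 20% in section 10.2 is recruitment and screening failure, not attrition.

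**The plan's own figures.** For 60 per arm and a difference of 0.37, power is 78.2% by normal approximation and 77.5% by noncentral t (stated 78%). For 80 per arm and 0.30 it is 72.7% and 72.2% (stated 73%). The power statement is not in error.

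**Expected LOCF estimate.** With drop-out p1 (app) and p0 (control) unrelated to outcome, control change d and true effect 0.30:

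LOCF estimate = (1 − p1)(d + 0.30) − (1 − p0)d

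With p1 = p0 = p this is (1 − p) × 0.30, whatever d is: 0.9 × 0.30 = 0.27 and 0.8 × 0.30 = 0.24.

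**Interval width.** With complete data the residual variance is 0.74² × (1 − 0.5²) = 0.4107, and the width is 2 × 1.975 × √(0.4107 × 2/80) = 0.400. Under LOCF with equal drop-out p the pooled slope is s = (1 − p)r + p, and the residual variance is

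0.74² × [(1 − p)((r − s)² + 1 − r²) + p(1 − s)²] + ½p(1 − p) × 0.30²

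- p = 0.10: s = 0.55; 0.5476 × 0.6975 + 0.0041 = 0.3860; standard error 0.0982; width 0.388.
- p = 0.20: s = 0.60; 0.5476 × 0.64 + 0.0072 = 0.3577; standard error 0.0946; width 0.374.

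The interval narrows as data are lost.

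**Equal, non-informative drop-out (simulation).**

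| Drop-out per arm | LOCF estimate | Coverage | Power, LOCF v by-arm imputation |
|---|---|---|---|
| 10% | 0.27 | 93 to 94% | 77% v 78% |
| 20% | 0.24 | 90% | 71% v 74% |

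Type I error at 20% is 4.8%. Coverage at 20% is 92% if r = 0.3 and 87% if r = 0.7. For subscale 2 with a true difference of 0.4 × 0.54 = 0.216, LOCF gives 0.194 and 0.173, with coverage 94% and 90%.

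**Unequal drop-out with a rise in both arms.**

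| App / control | Rise d | LOCF estimate | Coverage |
|---|---|---|---|
| 15 / 10% | 0.15 | 0.85 × 0.45 − 0.90 × 0.15 = 0.25 | 92% |
| 10 / 15% | 0.15 | 0.90 × 0.45 − 0.85 × 0.15 = 0.28 | 95% |
| 25 / 15% | 0.15 | 0.75 × 0.45 − 0.85 × 0.15 = 0.21 | 83 to 85% |
| 30 / 10% (stress) | 0.30 | 0.70 × 0.60 − 0.90 × 0.30 = 0.15 | 66 to 68% |
| 10 / 30% (stress) | 0.30 | 0.90 × 0.60 − 0.70 × 0.30 = 0.33 | 94% |

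Upward bias needs p0 > p1 and d above p1 × 0.30/(p0 − p1). At 10/30% that is 0.1 × 0.30/0.2 = 0.15; at 10/15% it is 0.1 × 0.30/0.05 = 0.60.

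Type I error with a 0.15 rise is 5.1% (15/10%) and 5.6% (25/15%). With a 0.30 rise it is 5.9% (25/15%), and 9.7 to 9.8% with a 20-point gap.

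**If drop-outs keep only a share g of the completers' gain (20% per arm).** The true effect is 0.30 × (0.8 + 0.2g).

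| g | True | LOCF (coverage) | Imputation (coverage) |
|---|---|---|---|
| 0 | 0.24 | 0.24 (95%) | 0.30 (92%) |
| 0.5 | 0.27 | 0.24 (94%) | 0.30 (94%) |
| 1 | 0.30 | 0.24 (90%) | 0.30 (95%) |

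**Total error.** At g = 1 and r = 0.5, LOCF's root-mean-square error is √(0.0982² + 0.03²) = 0.103 at 10% and √(0.0946² + 0.06²) = 0.112 at 20%. Observed-case ANCOVA, the missing-at-random comparator, gives 0.108 and 0.113. LOCF is worse at r = 0.7 with 20% drop-out (0.098 v 0.094) and at 25/15% with a 0.15 rise (0.132 v 0.114).

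**The case against.** The strongest reply is that the plan already covers this. Pattern-mixture analyses for attrition are promised at high and low values, so a serious LOCF bias would show there. That stands as mitigation. It does not change the main estimate, p-value or interval, and because the shifts are unstated they could be chosen after the data are seen.

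It can also be said that imputation swaps one untestable assumption for another, when section 10.4.2 itself regards not-at-random missingness as plausible. The synopsis leaves it to users whether to open the app at all, so little gain among drop-outs is not far-fetched, and in that case LOCF is right. This stands, and is why the fix needs a no-change case. Nor is imputation more accurate overall: with equal drop-out and r = 0.5, LOCF's total error is no worse. The case against LOCF is bias, coverage and hidden uncertainty.

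Three stronger readings are tempting and are not supported:

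- A reader might infer that LOCF makes the test invalid. Type I error is clearly raised only with a 20-point drop-out gap and a 0.30 rise in both arms, and the documents support neither value.
- A reader might infer which arm will lose more people. Section 6.5 gives app users with their own device a "gift card at baseline to offset network expenses", and others a tablet. Section 11.1.4 (Step 7) has inactive accounts followed up. But the end-of-study card in 6.5 goes to everyone, "whether they are in the control group or are in the intervention group". Weekly control mailings cannot be taken as settled: Step 7 describes them, while sections 15.7 and 15.7.4 describe one set sent with the welcome letter. Those sections must be reconciled.
- A reader might infer that a shrunken estimate will missize the later trial. The documents say the pilot gives preliminary data and design information, not that the later trial will be sized on this estimate.

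**Conclusion.** The point holds and should be fixed. With one post-baseline assessment, LOCF sets each drop-out's three-month score to the pre-treatment score, no reason is given, and the interval is too narrow for the information lost.

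Under the stated assumptions, equal non-informative drop-out costs 0.03 of a 0.30 effect at 10% and 0.06 at 20%, mainly as bias and lost coverage, with little effect on power or type I error. Unequal drop-out with rising scores can bias the estimate in either direction, or the biases can offset. On bias alone, LOCF is the closer method only if drop-outs keep less than half of the completers' gain. The direction and size in this trial cannot be known from the documents, which give no attrition rate, expected change or correlation.

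**What to change.** In section 10.4.2, make the primary analysis ANCOVA with follow-up scores multiply imputed by arm from the baseline HLQ score. Add at most a few low-dimensional covariates, for example age and collapsed education. The full category sets in section 15.9.4 would be too many for about 0.8 × 80 = 64 completers per arm at 20% drop-out.

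Keep the pattern-mixture analyses as the not-at-random sensitivity, with shift values stated in advance and a no-change-after-drop-out case among them. Keep LOCF as supplementary at most. Report drop-out by arm. Section 10.4.3 follows by reference. Separately, section 9.1 must be reconciled with sections 15.6.2 and 15.9 on whether the PDSMS is collected at baseline.

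The edit is one paragraph and one line, and both methods are already in the plan. With baseline HLQ as the only predictor, intervals are about 10% wider than LOCF at 10% drop-out (0.427/0.388 = 1.10) and 22% wider at 20% (0.457/0.374 = 1.22). Part of that is uncertainty LOCF hides. With about 18 extra terms per arm the widths are 0.449 and 0.509, about 16% and 36% wider. The estimate would then rely on missing at random. If drop-outs gain nothing, it overstates the effect by 0.30 − 0.24 = 0.06 at 20% drop-out, which the no-change case would show.
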